#### REVISION HISTORY

Revision #	Version Date	Summary of Changes	Consent Change?
1.2	9/19/2019	Response to stipulations following IRB from 9/13/2019. Clarifications regarding provider consent for case script field testing, contact information for study team, details on terms of study termination, details of clinic visits, and procedures for informing SPs of what to expect as part of the job.	Yes
1.3	11/04/2019	Adopted alternative approach to recruitment and maintenance of CABs based on local input.	Yes
1.4	12/1/2020	Amended clinic recruitment procedures (12.1) to reflect the assistance we are now receiving from the Guangzhou CDC and to record the actual number of clinics in our sample pool (46 instead of 81)	Yes
1.5	1/5/2021	Amended the consent procedures (22.1 and 22.3 sections): Waiver of written consent	Yes
1.6	1/12/2021	Added a new qualitative research component: Aiming to study how the SPs' background, sexual identity and LGBT community experience play a role in their study engagement and potentially change after the participation, by conducting interviews before and after their clinic visits:  Study endpoints (3.2): Inserted the description of the endpoints/findings we expect from this qualitative interview  Procedures involved (5.2): Illustrated the main change on the study procedures in the preparatory stage  Consent process (22.1): Illustrated the add-on consenting process for this particular purpose	Yes

PROTOCOL TITLE: Standardized Patients to Address Intersectional Stigma  
VERSION DATE: 07/23/2019

1.7	2/17/2021	Added a clause in consent procedures pertaining to qualitative sub-study indicating that participation is voluntary and will not impact their work as an SP.	Yes
1.8	5/27/2021	The measurement tools (SP scripts and healthcare checklist) were revised to reflect the suggestions provided by the recruited SPs and volunteer clinicians during the training. The changes were notified to the SP members (p13).	No
2.0	7/29/2021	Updated the version 1 protocol to include new descriptions of the phase 2 research which includes the RCT related activities such as the intervention design and implementation, as well as collection of follow-up data.	No
2.1	11/02/2021	Update the payment details for participants, clarified logistics for the qualitative interviews.  Consent forms revised to remove any language pertaining to arm, as well as to include information about the hybrid training design and participant compensation.	Yes
2.2	09/01/2022	Update the data banking plan in section 6	Yes

PROTOCOL TITLE: Standardized Patients to Address Intersectional Stigma  
VERSION DATE: 07/23/2019

#### **ABBREVIATIONS/DEFINITIONS**

[figure not shown]
CAB	Community advisory board
EOC	Erosion of care
MSM	Men who have sex with men
GDCDC	Guangdong Center for STD Control and Prevention
PLWH	People living with HIV/AIDS
RCT	Randomized control trial
RERI	Relative excess risk due to interaction
ROR	Return of results
SMC	Safety monitoring committee
SP	Standardized patient
STD	Sexually transmitted disease

## 1.0 Objectives

### 1.1 Purpose

This is the second phase of a two-phase study that aims to develop and evaluate an intervention to reduce enacted stigma in healthcare settings aimed at PLWH and MSM in China. The **1) preparatory phase** consists of collecting baseline data and conducting formative research in order to inform design of the **2) RCT phase** of research. Although funding for both the preparatory and RCT phases have been secured, we developed study protocols for each phase in an iterative fashion to ensure the opportunity to properly incorporate results from the preparatory phase into the final design of the RCT. The overall scheme of the two study phases are illustrated in Figure 1 below.

**Figure 1. Schemata for overall study design.**

Having completed all preparatory phase activities, this protocol will describe activities related to the **RCT phase** which will be conducted in two stages:

**Stage 1 of the RCT Phase: Implementation of the stigma reduction intervention.** A three-module provider training course designed during the preparatory phase will be administered to consenting providers employed at clinics randomized to the treatment arm of the study. The first module will be administered as a one-day training on site at the Guangdong Center for STD Control and Prevention. This will be followed by two online modules that provider participants will complete on their own. Design of this intervention has been informed by results of the baseline study and incorporates expert input from members of our community advisory boards (CAB), one made up of community members and the other of providers. Content of the intervention will include knowledge and skills training on topics including clinical management of common STIs, shared decision making, sexual history taking, and working with non-traditional/marginalized populations. Training methods for the onsite training will include didactic lectures, group-based discussion, and medical simulation and feedback with trained SPs. Methods for the online follow-up sessions will include webinars, short training videos, and multiple choice quizzes.

**Stage 2 of the RCT Phase: Follow-up data collection.** Follow-up collection using the same unannounced SP visit approach as in the baseline data collection will take place within 1-3 months of the end of the stigma reduction intervention. Briefly, this will consist of working with trained actors who are recruited from the community, who receive training to conduct unannounced clinic visits with consenting providers for the purposes of observing their clinical performance. SPs

will present clinically standardized case scenarios, but the HIV status and sexual orientation of each case will be randomly varied in order to quantify the extent to which HIV stigma and/or homophobia potentially contribute to the deterioration of care quality. Enrolled providers already provided their consent for both rounds of unannounced clinic visit during the preparatory phase of research.

Research activities in all phases of the project will take place in Guangzhou, China.

## 2.0 Background

### 2.1 Significance of Research Question/Purpose

Consistent data highlight the central role of stigma in limiting uptake of HIV related testing, treatment, and care. This is particularly true for gay, bisexual, and other MSM who have the lowest rates of engagement with the healthcare system despite bearing the highest HIV incidence burden. Particularly for MSM seeking HIV testing services, enacted stigma—acts of discrimination or hostility directed at a person because of their perceived stigmatized status—both on account of their same-sex behaviors (i.e. sexuality stigma or homophobia) and the perception of their elevated HIV risk (HIV stigma) is all too common.

A major challenge to date in reducing healthcare stigma is our limited ability to measure it. Numerous interventions for providers, for example, have assessed program impact by comparing participants' self-reported attitudes towards PLWH before versus after the intervention, a measure fraught with social desirability bias. Documentation of patient experiences in clinical settings, though less subject to social desirability, may suffer recall bias and also lack standardization across patients. Inability to observe the very behaviors they seek to change also limits the design of these interventions from using insights beyond theoretical reasoning to specify the underlying causes and solutions of stigma.

By contrast our experimental SP audit method provides a window of insight into provider behaviors *as they unfold in real clinical settings*, providing an objective and standardized measure of stigma amenable to comparison across studies and settings. Our SPs will be recruited from among MSM living locally, whose group makeup will be managed to reflect the overall characteristics of the local MSM community in terms of age, ethnicity, and socioeconomic status. SPs will be trained to consistently present a standardized case to providers. Using an experimental audit design, we will randomly vary the HIV infection status and sexual orientation of all of our SPs. Stigma will be evaluated by comparing the quality of care that SPs experience during provider visits. Quality of care will be measured by administration of a standard of healthcare checklist to SPs following each visit, and which will include items related to provider behaviors including the types of questions asked, accuracy of the preliminary diagnosis, body language and bedside manner (checklist included in Appendix 1). Differences in tallied aggregate scores across SP visit scenarios (e.g. HIV positive versus HIV negative presentations) will be quantified as the enacted healthcare stigma attributable to the condition in question (i.e. HIV infection). In addition, SPs will participate in post-visit “debrief sessions” with another member of the study staff immediately following each visit to recount any other possible features of the visits—both positive and negative—not accounted for in the healthcare quality checklist. This method of quantifying stigma will not be used to identify individual providers or

PROTOCOL TITLE: Standardized Patients to Address Intersectional Stigma  
VERSION DATE: 07/23/2019

instances of poor treatment but rather to characterize population level incidence and patterns of stigma enacted by providers towards vulnerable patients. Lastly, the impact of the intervention on overall HIV testing volumes in study facilities will also be evaluated by examining aggregate counts of facility-level HIV tests conducted during the baseline and follow-up observation periods. This information will be provided by the laboratory departments of all participating facilities. This technique of data collection has been successfully piloted with a clinic-based intervention administered by the GDCDC.

In the final step of the initial preparatory phase of this project, we conducted a preliminary and descriptive analysis of the SP-collected baseline clinic visits in order to characterize the nature and patterns of enacted healthcare stigma towards PLWH and MSM. Results quantified the amount of HIV and sexual stigma observed in study clinics (further details of the outcome in Section 3.0), and also stratified results by broadly descriptive characteristics such as age, sex, and rank of provider. These results were shared in Return of Results (RoR) sessions with members of community advisory boards (CABs), one made up of MSM and the other of providers through separate share back sessions. We convened meetings with CAB members to solicit their insights about drivers of provider behaviors observed in their community. The team incorporated CAB feedback to develop the intervention, a stigma reduction training program for provider participants employed at clinics randomized to the treatment arm. Details of the final design were informed by feedback from study team members and each of the two CABs, the overall structure consists of didactic content as well as experiential learning using simulation-and-feedback sessions with trained SPs. We may re-consult our CABs at later stages of the design for iterative feedback on any adjustments made to the intervention design.

**In the RCT phase of this project, covered by the current protocol,** we will administer the intervention to all consented and enrolled providers employed at study clinics randomized to the treatment arm. We will also conduct a second round of unannounced SP clinic visits to collect follow-up data in order to estimate the impact of the intervention on provider behaviors. The intervention design is largely informed by the Information-Motivation-Behavioral Skills model of behavior change as well as by input from the two CABs during the return of result sessions. The finalized version of the intervention is expected to take a hybrid form consisting of both in-person, onsite sessions and self-directed online sessions for participants to complete in their own time within a specified window of time. Within 1-3 months following the stigma reduction intervention, unannounced SP clinic visits will recommence using the same procedures and data collection techniques as for the baseline visits. Data from the healthcare quality checklists will be integrated into a score for each visit and used to estimate the impact of the stigma reduction intervention. Facility level information on HIV testing will also be collected in the form of aggregate counts as a secondary outcome in order to compare testing volume in the baseline versus follow-up observation periods.

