#### 3.2 Secondary Endpoint(s)/Event(s)/Outcome(s):

Three secondary endpoints will be collected.

The first will take the form of findings from debrief sessions (i.e. structured interviews) with SPs that will be administered by another study team member immediately following each unannounced visit. This qualitative data is intended to identify emergent episodes of adverse care not captured by the healthcare quality checklist used to quantify the primary endpoint. Findings will take the form of a written report to describe patterns and themes emergent in the interviews, with direct quotes to illustrate concepts where helpful.

The second endpoint will be the aggregate clinic-level number of HIV tests conducted in each enrolled clinic during the study period. This data will be abstracted from the provincial case report system.

The third endpoint will be the qualitative data collected through in-depth interviews with our SPs after their participation in each round of clinic visits (baseline and follow-up). The collected data will provide insight into how their sexual identity and experience in community activities may motivate their participation in a research project like ours, and how they may change their views regarding stigma after their study engagement. Findings will take the form of transcribed scripts of recorded interviews.

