## 5.0 Procedures Involved

### 5.1 *Study Design*

The design of the overall study is a pilot RCT to evaluate the preliminary effectiveness of the stigma reduction intervention developed in the course of the project, with randomization taking place at the facility level (cluster randomization). As activities related to the preparatory phase of research have been completed, the activities described below pertain only to the RCT phase.

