## **17.0 Data Management**

### **17.1 Data Analysis Plan:**

The primary goal of the study is to estimate the impact of healthcare stigma—in particular stigma directed at patients living with HIV (HIV stigma), patients who have same sex behaviors (homophobia), and patients with both attributes (intersectional stigma) on the quality of sexual healthcare they receive. Stigma is quantified as the difference in the mean healthcare quality index across the four case scenarios. Patterns of stigma occurrence are also assessed by stratifying results across key attributes such as tier of care (e.g. county hospital versus township clinic), rural/urban region, provider sex, and provider professional rank in order to illuminate provider subgroups of interest to inform tailored intervention design. A secondary analytical goal of this study is to assess the preliminary effect of the intervention on healthcare quality by comparing the same healthcare quality index across treatment arms. Details in the power analysis (section 17.2) and statistical analysis (section 17.3) sections are described separately for these two goals.

For the qualitative sub-study analysis, data from debrief session conducted with SPs following each clinic visits will be transcribed and translated into English by study staff and spot checked by the co-PIs for transcription accuracy by bilingual

PROTOCOL TITLE: Standardized Patients to Address Intersectional Stigma  
VERSION DATE: 07/23/2019

study staff. Co-PIs will oversee analysis by study staff including coding of transcripts and identification and interpretation of emergent themes.

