#### 17.2 Power Analysis:

**Stigma Quantification:** The primary objective of this pilot study is to estimate the extent to which stigma towards PLWH (HIV stigma) and towards MSM (homophobia) contribute to the deterioration of healthcare quality relative to straight people without HIV. A total sample size of 160 standardized patient (SP) interactions would provide 80% power (alpha=0.05) to detect a minimum effect size of 0.18 standard deviation. This calculation is conservative in that it does not account for blocked randomization of the SP cases within practices, which will lend additional power to each comparison. Two-sided tests will be needed to detect differences across the four case scenarios in order to separately quantify HIV, sexual, and intersectional stigma, for which the same assumptions will provide the same amount of power to identify a minimum effect size of 0.17 standard deviation between any 2 pairwise comparisons of scenarios. As recruitment will take place at the clinic level, the number of participants that will be needed to be recruited to the study will depend on estimates of the average numbers of eligible providers that our team can reasonably expect to recruit at each clinic. Preliminary data suggest that clinics in our study region employ an average of 5 eligible providers, of whom we conservatively expect to recruit 70% or 3.5 per clinic. Each provider will receive 3 unannounced visits from a standardized patient, yielding a final estimated pool of 56 providers for this study.

**Preliminary intervention effects:** A secondary goal of the RCT is to estimate the preliminary effect of the intervention on quality of care index observed by SPs. Though this is only a secondary goal, we determine that it is plausible that the target enrollment of 20 clinics randomly allocated to treatment and control in a 1:1 manner could yield sufficient power to detect reasonably small effects on the primary outcome measure. That is, with an alpha level of 0.05 for a one-sided test, an intra-cluster coefficient of 0.07, and a baseline prevalence of standardized quality of care index (with mean of 0 and standard deviation of 1), a sample size of 160 SP clinic visits (8 visits per clinic on average) would provide 80% power to detect a reduction in EOC scores due to the intervention as small as 0.17 standard deviations.

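### The HIV-testing endpoint has no between-arm analysis and two unreconciled data sources; the one comparison stated for it is baseline versus follow-up

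*Combined protocol and SAP*

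**What the plan says.** Section 2.1 gives the purpose: "the impact of the intervention on overall HIV testing volumes in study facilities will also be evaluated by examining aggregate counts", for the baseline and follow-up periods. Later in Section 2.1, the paragraph on the RCT phase says the counts are collected as a secondary outcome in order to "compare testing volume in the baseline versus follow-up observation periods". Neither place mentions the arms.

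Section 3.2 lists three secondary endpoints. Two are qualitative. The other is the "aggregate clinic-level number of HIV tests conducted in each enrolled clinic during the study period".

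The source is stated twice, differently. Section 2.1: "This information will be provided by the laboratory departments of all participating facilities", by a technique it describes as already piloted. Section 3.2: "This data will be abstracted from the provincial case report system".

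Section 17.1 describes the assessment of the intervention as "comparing the same healthcare quality index across treatment arms". Section 17.2 covers power for that index only. The intention-to-treat, two-stage least squares and script-interaction models in Section 17.3 all have the index as outcome. HIV test counts appear in none of these sections.

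**The concern.** Section 2.2 gives as the project's central hypothesis that remedying stigma will lower barriers to HIV testing. The test count is the only endpoint that bears on testing itself. Clinics are randomised and counts are to come from all of them, so concurrent control data will exist, but the comparison as worded does not use them.

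The two periods are also well apart. Baseline visits belong to the preparatory phase, which Section 1.1 says is complete. Section 8.1 then allows 15 months for intervention development, delivery and follow-up. General changes in demand, policy or laboratory practice over such an interval would enter a before-after estimate in full. The unreconciled source and undefined windows add a second problem: the counts may not be comparable across periods or clinics even if the right contrast is chosen.

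**Working it through.** The plan gives no rate, variance, power or effect size for HIV test counts, so there is no figure of its own to reproduce. The check has two parts.

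**1. The text side by side**

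| Item | Section 2.1 | Section 3.2 | Sections 17.1–17.3 |
|---|---|---|---|
| Purpose | Impact of the intervention | Not stated | Not mentioned |
| Comparison | Baseline v. follow-up | None | None |
| Window | Two observation periods, undated | The study period as a whole | None |
| Source | Facility laboratories | Provincial case report system | None |

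No later section supplies the missing arm contrast, chooses between the sources or dates the windows.

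**2. What the stated comparison would do**

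Let every clinic's testing change by a factor 1 + g for reasons unrelated to training, and let training have no effect.

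- Before-after ratio in treated clinics: 1 + g. For g = +20% (assumed), 1.20; for g = −20%, 0.80.
- Between-arm ratio of changes: (1 + g)/(1 + g). For g = +20%, 1.20/1.20 = 1.00.

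For the error rate, take 10 clinics per arm, from "the target enrollment of 20 clinics randomly allocated to treatment and control in a 1:1 manner". Assume that clinic log changes are normal with mean ln(1 + g) and SD 0.15, 0.30 or 0.50. The tests, at two-sided alpha 0.05, are a one-sample t-test of the change (before-after) and a two-sample t-test of the change between arms. Share of 20,000 simulated null trials declared significant:

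| SD of log change | Common change g | Before-after, 10 treated | Before-after, all 20 | Between arms |
|---|---|---|---|---|
| 0.15 | 0% | 4.8% | 4.9% | 4.7% |
| 0.15 | 10% | 43.5% | 77.0% | 5.2% |
| 0.15 | 20% | 92.8% | 100% | 5.0% |
| 0.15 | 30% | 99.8% | 100% | 5.0% |
| 0.30 | 0% | 4.8% | 4.8% | 5.0% |
| 0.30 | 10% | 14.8% | 27.8% | 5.0% |
| 0.30 | 20% | 40.4% | 73.2% | 5.1% |
| 0.30 | 30% | 69.6% | 95.9% | 5.1% |
| 0.50 | 0% | 5.1% | 5.4% | 5.2% |
| 0.50 | 10% | 8.8% | 13.3% | 5.0% |
| 0.50 | 20% | 17.7% | 34.3% | 5.0% |
| 0.50 | 30% | 31.6% | 60.4% | 4.8% |

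With no common change, all three tests hold their level. With one, only the between-arm test does. Pooling all 20 clinics before and after makes matters worse, because the common change is then estimated more precisely.

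A change of data source between periods that affects all clinics alike acts like g: it biases before-after and cancels between arms. A source difference that varies by arm would bias both, so the choice of source matters whichever contrast is used.

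**The case against.** The strongest reply is that Section 2.1 is background prose, not an analysis specification. It describes the standardized-patient outcome in the same way, without mentioning arms, and Section 17.3 then analyses that outcome between arms with baseline adjustment. Baseline and follow-up counts in every randomised clinic are also exactly what a baseline-adjusted or difference-in-differences analysis needs. Section 2.4 defers a comprehensive data analysis plan until before analysis starts. Finally, this is a secondary endpoint in a pilot, and no power calculation depends on it.

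Much of this stands. A reader might infer that the investigators have chosen a before-after analysis and will discard the randomisation. The documents do not show that: nothing rules out an arm contrast, and strictly no analysis is specified. A reader might also infer that the source switches between periods. No section assigns either source to a period; the two sections simply disagree about the endpoint as a whole. And a reader might infer from its name that the provincial system records cases and not tests. The documents do not describe its contents, and Section 3.2 says tests conducted are what will be abstracted from it.

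What the reply does not do is fill the gap. For the quality index, Section 17.3 repairs the silence of Section 2.1; for test counts nothing does. The deferred plan is not part of these documents.

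**Conclusion.** The point holds as a gap in specification with a conditional bias. Firm from the text: an endpoint meant to show intervention impact has no between-arm analysis, its only stated comparison is temporal, its two source statements conflict, and its windows are undefined.

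Conditional: if it is analysed as worded, a common change in testing could be taken for an effect of training. Its size equals the common change, so an assumed range of −20% to +20% gives a spurious ratio of 0.80 to 1.20. For an assumed 20% rise, false significance in the 10 treated clinics runs from about 18% to 93% over the assumed SDs, against about 5% between arms. The trend and the SDs are assumptions, because the plan gives neither; the cancellation between arms needs only that the change be common to both.

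The primary endpoint is unaffected. The matter should be settled before the counts are analysed, but it does not threaten the trial as a whole.

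**What to change.** 1. In Sections 3.2 and 17.3, replace the baseline-versus-follow-up comparison with a between-arm comparison of follow-up HIV tests per unit time, adjusted for each clinic's baseline count. A count model with time at risk as offset would serve, as would a log rate with a stated rule for zero counts. Bring Section 2.1 into line.
2. Base inference on the clinic, with a small-sample correction or a permutation test over the 20 clinics that follows the allocation scheme actually used.
3. Define the baseline and follow-up windows by date or by length and timing, the same for both arms.
4. Reconcile Sections 2.1 and 3.2 on the source. Name one source of tests performed and use it for both periods and both arms. The laboratory counts are a natural candidate, since Section 2.1 reports that technique as piloted.

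Cost: SAP wording and one extra model on data already planned for collection.
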